6.6. Safety Analysis

Descriptive statistics will be calculated for quantitative safety data and frequency counts will be compiled for classification of qualitative safety data. The safety population will be used for these analyses.

Adverse Events:

The subject incidence of treatment-emergent adverse events (TEAE) will be summarized overall, by severity, and by attribution.

Clinical Laboratory Results:

Shifts in clinical laboratory parameters from baseline to worst post-baseline grade will be provided.

Vital Signs:

The subject incidence of >5% weight loss or gain on study will be provided, as well as whether weight loss was explained or unexplained.

6.7. Efficacy Analysis

The Primary Efficacy Endpoint will be tested in all randomized subjects and defined as:

• The proportion of all randomized subjects who attain IGA Success, defined as a vIGA-AD score of 'clear' or 'almost clear' PLUS a 2-grade improvement from Baseline at Week 4

Upon demonstration of statistical significance for the primary endpoint, a hierarchical testing scheme will be used to test the key secondary endpoint defined as:

• The proportion of randomized subjects with a vIGA-AD score of 'Moderate' at randomization who attain IGA Success at Week 4

Missing IGA scores will be imputed using multiple imputation.

Upon successful demonstration of statistical significance for the secondary endpoint, the remaining endpoints will be grouped into secondary endpoint family 1, comprised of the 4-point reduction on the WI-NRS, and secondary endpoint family 2, comprised of the EASI-75 at Week 4, vIGA-AD of 'clear' or 'almost clear' at Week 4, time to achievement of vIGA-AD success, and time to achievement of EASI-75. An alpha level of 0.03 will be used to test the 4-point reduction in the WI-NRS at Week 4. An alpha level of 0.02 will be used to test the endpoints in secondary endpoint family 2. The Holm procedure will be used to control for multiple comparisons within secondary endpoint family 2. The endpoints listed below will be tested among all randomized subjects, unless otherwise noted.

Secondary Endpoint Family 1 (α=0.03)

• Among subjects with baseline WI-NRS ≥ 4, the proportion of subjects who attain a 4-point reduction in the WI-NRS at Week 4

Secondary Endpoint Family 2 ($\alpha = 0.02$, Holm's procedure)

- The proportion of subjects who attain at least a 75% reduction in the Eczema Area and Severity Index at Week 4 (EASI-75)
- Proportion of patients with vIGA-AD score of 'clear' or 'almost clear' at Week 4
- Time to achievement of vIGA-AD success
- Time to achievement of EASI-75

The ITT population will be used for the primary and secondary efficacy analyses, with the exception of the key secondary endpoint analysis which will be performed on the vIGA-AD Moderate ITT population.

6.8. Adverse Events

All TEAEs occurring during the study will be recorded and classified on the basis of MedDRA terminology for the safety population. TEAEs are defined as those AEs with an onset on or after the time of first study drug application. All reported TEAEs will be summarized by treatment group.

Descriptive statistics will be calculated for quantitative safety data and frequency counts will be compiled for classification of qualitative safety data.

Adverse Events:

The subject incidence of treatment-emergent adverse events (TEAE) will be summarized overall, by severity, and by attribution.

Clinical Laboratory Results:

Shifts in clinical laboratory parameters from baseline to worst post-baseline grade will be provided.

Vital Signs:

The subject incidence of >5% weight loss or gain on study will be provided, as well as whether weight loss was explained or unexplained.

6.9. Body Surface Area

Body surface area (BSA) affected by AD will be analyzed descriptively.

6.10. Local Tolerance Assessment

For Investigator's assessment, the numeric application site reaction scores will be summarized individually by using number and percentage of subjects by visit, as well as mean/median scores.

6.11. Medical History and Physical Examinations

Medical history for all subjects will be presented descriptively by parameter.

Physical examination for all subjects will be presented descriptively by parameter. Changes in physical examinations will be described in the text of the final report.

6.12. Clinical Laboratory Results and Vital Signs

All clinical laboratory results and vital signs measurements and their change from baseline (pre-dose), will be summarized descriptively by parameter, visit, and treatment group along with time point of collection.

A shift table describing out-of-normal range shifts will be provided for clinical laboratory results.

A shift table will identify subjects who gain or lose >5% body weight over the course of the study.

6.13. **Prior and Concomitant Medications**

Prior and concomitant medication information for all randomized subjects will be presented in a by-subject listing. Summary tables will be presented by World Health Organization-Anatomical Therapeutic Chemical Classification System (WHO-ATC) therapeutic category and product.

6.14. Subject Reported Outcomes Analyses

WI-WI-NRS scale will be analyzed for change from Baseline (measured as a weekly average during the week before the Baseline/Day 1 visit) in itch severity of at least 4 at Week 4/Day 29 as a weekly average during the week before the Week 4/Day 29 visit.

6.14.1. Dermatology Life Quality Indexes, Children's Dermatology Life Quality Index, SCORAD and POEM

Dermatology Life Quality Index (DLQI), Children's Dermatology Life Quality Index (CDLQI), the Dermatitis Family Impact (DFI), the Scoring Atopic Dermatitis (SCORAD), and the Patient-oriented Eczema Measure (POEM) will be analyzed by evaluation of the reduction in total score at Week 4. These efficacy endpoints will be analyzed descriptively.

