5.2.3. Worst Itch Numerical Rating Scale (WI-NRS)

The WI-NRS has been developed as a simple, single item to assess the patient-reported severity of this symptom at its highest intensity during the previous 24-hour period. (Newton 2019). The WI-NRS will be determined by the subject's recording of daily assessment of worst itch over the past 24 hours. The scale is from '0 to 10' ("no itch" to "worst itch imaginable" or "worst imaginable itch").

WI-NRS Assessments will be performed according to the Schedule of Visits and Assessments (Section 1.3) starting 7 days prior to the Baseline/Day 1 clinic visit (during the 7 days prior to Baseline/Day 1 the subject will record the WI-NRS value every day).

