5.2 Baseline

Unless otherwise specified, baseline value will be defined as the last non-missing assessment prior to or concurrently with the first study treatment dosing (including unscheduled/retest assessments). If the last non-missing assessment is performed on the same date as the first study treatment administration and time is not available, it is assumed that the assessment took place prior to IP application, per study site training, and the assessment will be considered as baseline, except for adverse events (AEs) and medications starting on the first study treatment dose administration date which will be considered postbaseline.

Average weekly baseline WI-NRS is defined as the average of all non-missing scores reported during the last 7 days prior to treatment if at least 4 of 7 evaluable daily WI-NRS questionnaires

	STATISTICAL ANALYSIS PLAN, Version 1.0
Protocol Number: ARQ-151-312	Sponsor: Arcutis Biotherapeutics, Inc.

available. Daily baseline WI-NRS is defined as the last non-missing assessment prior to or concurrently with the first study treatment dosing. Day 1 WI-NRS score will be used to calculate the value for week 1 only when it is collected after the application of the first study drug. If Day 1 WI-NRS score is collected prior to or concurrently with the application of the first study drug, then the Day 1 WI-NRS score will be included in baseline calculation.

For investigator/subject tolerability assessments, baseline is derived as the measurement taken on the day of first application of study drug.

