5.5 Derived Variables

All questionnaire scores will be derived by Biostatistics in the ADaM datasets using the formulas defined below, even if calculated scores are present in the EDC database. All pre-calculated scores will be ignored for analysis.

- vIGA-AD Success = vIGA-AD of 'Clear' (0) or 'Almost Clear' (1) plus at least a 2-grade improvement from Baseline.
- Average weekly WI-NRS = Average weekly of the WI-NRS pruritus scores will be
 calculated as the sum of the daily WI-NRS scores reported during a specific week (in a 7day period) of the study divided by the number of days with non-missing scores for that
 week. A minimum of 4 days of observations are needed to calculate average weekly WINRS. Otherwise, the corresponding average weekly WI-NRS will be considered missing.

	STATISTICAL ANALYSIS PLAN, Version 1.0
Protocol Number: ARQ-151-312	Sponsor: Arcutis Biotherapeutics, Inc.

The average weekly WI-NRS results will be presented for analysis visits i.e., Baseline, Week 1, Week 2, Week 3, and Week 4 (see Table 1 Table 4 for the analysis window).

• WI-NRS 4-point reduction = achievement of a 4- point reduction in average weekly WI-NRS pruritus score compared to average weekly WI-NRS baseline, calculated only for the subjects ≥12 years old with average weekly WI-NRS score of ≥ 4 at baseline.

$$\begin{split} \bullet \quad & \text{EASI total score} = 0.1 \; (E_h + I_h + E_{Xh} + L_h) \; A_h + 0.2 \; (E_u + I_u + E_{Xu} + L_u) \; A_u \\ & \quad + 0.3 \; (E_t + I_t + E_{Xt} + L_t) \; A_t + 0.4 \; (E_l + I_l + E_{Xl} + L_l) \; A_l \\ & \quad \text{for subjects $`\geq 8$ years old} \\ & \quad \text{and} \\ & \quad 0.2 \; (E_h + I_h + E_{Xh} + L_h) \; A_h + 0.2 \; (E_u + I_u + E_{Xu} + L_u) \; A_u \\ & \quad + 0.3 \; (E_t + I_t + E_{Xt} + L_t) \; A_t + 0.3 \; (E_l + I_l + E_{Xl} + L_l) \; A_l \\ & \quad \text{for subjects < 8 years old} \end{split}$$

where E, I, Ex, L, and A denote erythema, induration, excoriation, lichenification, and area, respectively, and h, u, t, and l denote head, upper extremities, trunk, and lower extremities, respectively. If a subject turns 8 years old during the study, the formula used at Screening will continue to be used through the study duration of the subject's participation in the study. Scalp, palms, and soles may be treated with investigational product in this study but will be excluded from the EASI assessment.

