For each categorical exploratory efficacy endpoint, count and percentages of subjects meeting the criteria for an exploratory efficacy endpoint will be presented by visit and treatment group based on observed data in the ITT population along with a 95% Wilson CI. Additionally, count and percentage of subjects meeting the criteria for vIGA-AD of Clear (0), EASI-50, EASI-90, and EASI-100 at Week 1 and Week 2 will also be presented by visit and treatment group based on observed data in the ITT population along with a 95% Wilson CI.

Continuous exploratory efficacy endpoints will be analyzed at Week 1, Week 2, and Week 4 and for daily WI-NRS assessments using an analysis of covariance (ANCOVA) with the factors of treatment, two stratification variables (pooled study site and randomized vIGA-AD score), and baseline of the variable under analysis as covariate. Statistical comparisons between the treatment groups will be obtained using contrasts. The Least Square (LS) mean and its standard error,

	STATISTICAL ANALYSIS PLAN, Version 1.0
Protocol Number: ARQ-151-312	Sponsor: Arcutis Biotherapeutics, Inc.

difference in LS means between treatment group (i.e., active - vehicle), its standard error and associated 95% confidence interval, and p-value for difference from vehicle will be presented at each visit. These analyses will be performed based on observed data in the ITT population.

Categorical exploratory efficacy endpoints at Weeks 1, 2, and 4 will be analyzed using a CMH test adjusted for the two stratification variables (pooled study site and randomized vIGA-AD score). Common MH odds ratio, common MH proportion difference and their common associated 95% CI, adjusted for the randomization factors, will be provided. The p-value will be from a CMH test for the common MH odds ratio, unless the common MH odds ratio is not estimable. In such circumstances, the p-value will be from a MH test for the common MH proportion difference.

The analysis of these endpoints will be performed on the observed data with no imputation. The p-values will be nominal as no formal inferential testing will be done on exploratory efficacy endpoints.

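### The exploratory daily WI-NRS ANCOVAs adjust for one pre-dose itch score only; adding the mean of the pre-dose diary week as a second covariate would gain some precision at almost no cost

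*Protocol*

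**What the plan says.** **Data collected.** Protocol 5.2.3 asks for a diary score each day in the week before dosing: "during the 7 days prior to Baseline/Day 1 the subject will record the WI-NRS value every day".

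**Weekly itch.** Protocol 6.14 describes the four-point responder analysis at Week 4, with a weekly average at both ends. Its baseline is the one in "change from Baseline (measured as a weekly average during the week before the Baseline/Day 1 visit) in itch severity". SAP 5.2 matches this: "Average weekly baseline WI-NRS is defined as the average of all non-missing scores reported during the last 7 days prior to treatment". SAP 5.5 sets the completeness rule: "A minimum of 4 days of observations are needed to calculate average weekly" WI-NRS. The Family 1 endpoints (SAP 6.5 and 12.2) use this averaged baseline.

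**Daily itch.** SAP 5.2 defines a second baseline: "Daily baseline WI-NRS is defined as the last non-missing assessment prior to or concurrently with the first study treatment dosing". SAP 12.3 analyses the continuous exploratory endpoints, daily WI-NRS included, by ANCOVA on observed data. The terms are treatment, pooled site, randomized vIGA-AD score and "baseline of the variable under analysis as covariate". For daily WI-NRS that covariate is the single last pre-dose score, and no other itch covariate is listed. SAP 12.3 treats the p-values as nominal.

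**The concern.** A single 24-hour worst-itch score is a noisy reading of how itchy a subject usually is. Up to seven such scores are available before dosing, and the daily ANCOVA uses one. Between-subject variation that the other scores could explain stays in the error term, so the daily treatment differences have wider confidence intervals than the collected data allow. SAP 12.3 commits to reporting a difference, standard error, 95% CI and nominal p-value for these comparisons, so precision has some value even though nothing confirmatory depends on it. What is at stake is efficiency; randomization keeps the comparison fair with either covariate set.

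**Working it through.** **Inputs.** From the documents: up to 7 pre-dose daily scores; one of them, the last, in the model; outcomes on Days 1 to 28. The documents give no variance, correlation or power for daily WI-NRS, so there is no stated figure to reproduce and the size must be assumed.

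**Assumed model.** Total variance is 1. Each subject has a stable level with variance share b. Day-to-day deviations have variance 1 − b and first-order autocorrelation ρ. The grid is b = 0.4, 0.6, 0.8 and ρ = 0, 0.3, 0.6, 0.8. The lag d from the last pre-dose score runs from 1 to 28 days. The first post-dose score has d = 1: under SAP 5.2 and Table 4 it falls one day after the last pre-dose score, either Day −1 to Day 1 or pre-dose Day 1 to Day 2.

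**Formulas.** Let L be the last score and M the 7-day mean. c_L and c_M are their covariances with the outcome, v_M is the variance of M, and v_LM is the covariance of L and M.
- L only: residual = 1 − c_L²
- L and M: residual = 1 − (c_L²·v_M − 2·c_L·c_M·v_LM + c_M²) / (v_M − v_LM²)

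Sample size, allocation and the score's SD cancel in the ratio of the two.

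**Central case, b = 0.6, ρ = 0.3.** v_M = 0.6961. v_LM = 0.6 + 0.4 × 1.4283/7 = 0.6816. The denominator is 0.6961 − 0.6816² = 0.2315.
- First day (d = 1): c_L = 0.6 + 0.4 × 0.3 = 0.72 and c_M = 0.6 + 0.4 × 0.4285/7 = 0.6245. L only: 1 − 0.5184 = 0.4816. L and M: 1 − (0.3609 − 0.6129 + 0.3900)/0.2315 = 0.404. Ratio 0.84, a cut of 16%. The standard error ratio is √0.84 = 0.92.
- Later days: c_L and c_M both approach 0.6. L only: 0.64. L and M: 1 − 0.36 × (0.6961 − 1.3632 + 1)/0.2315 = 0.482. Ratio 0.75, a cut of about 25%. The standard error ratio is 0.87.

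**Independent days, ρ = 0.** Once M is in, L adds nothing, and the comparison reduces to 1 − b² against 1 − 7b²/(1 + 6b):

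| b | L only | L and M | ratio |
|---|---|---|---|
| 0.4 | 0.840 | 0.671 | 0.798 |
| 0.6 | 0.640 | 0.452 | 0.707 |
| 0.8 | 0.360 | 0.228 | 0.632 |

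**Whole grid.** The ratio runs from 0.632 (b = 0.8, ρ = 0) to 0.992 (b = 0.4, ρ = 0.8, first day), with median 0.828. That is a cut of about 1% to 37%, median 17%.

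**If levels shift after baseline.** The model carries each subject's level unchanged to Day 28. If the stable pre-to-post covariance is only 70% or 50% of that assumed, with total variance held fixed, the median cut falls to about 7% or 3%.

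**Adding against replacing.** Using M in place of L is not always better. In four settings with a subject effect, serial correlation and day-level noise, the ratio of M alone to L alone was 0.84 to 1.36 on Days 1 to 3 and about 0.82 to 0.98 from Day 7. Under pure serial correlation with no subject effect or noise, M alone was never better, with ratios up to 2.55. Keeping both avoids that loss: residual variance cannot rise when a covariate is added, and under the SAP's common-slope model the price is one degree of freedom.

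**The case against.** The strongest reply is that a daily outcome matched to a daily baseline is a standard choice, applied by one rule to every continuous exploratory endpoint, and that nothing important depends on it. Much of that stands.

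- **No conflict with the protocol.** A reader might infer from Protocol 6.14 that the SAP departs from a protocol-wide baseline. It does not. That section concerns the weekly-average four-point change at Week 4 and is silent on daily analyses.
- **Not the main evidence on onset.** A reader might take the daily ANCOVAs to be how the plan shows the speed of itch relief. Family 1 tests early response at Weeks 1 and 2 with alpha control, and average weekly WI-NRS has its own ANCOVA at Weeks 1, 2 and 4. Both rest on the averaged baseline. The daily series adds detail within weeks.
- **Gains are smallest on the earliest days**, when the last score is most informative.
- **Changing the baseline itself would cause trouble.** SAP 12.3 plans plots of mean daily score and of percent change. A different baseline would alter the denominator of percent change, so the choice would not be neutral there.
- **A further itch summary is created**, because a mean of available scores differs from the 4-of-7 rule.

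The last two points limit the remedy to an added covariate. None of them is a reason to leave the other pre-dose scores out of the model.

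**Conclusion.** The point holds as an optional efficiency improvement. SAP 12.3 with SAP 5.2 uses one of up to seven pre-dose scores in each daily WI-NRS ANCOVA. Adding their mean would lower residual variance by about 1% to 37% (median 17%) under the assumed model, and by a median of about 3% to 7% if subjects' levels shift differently after baseline. These figures rest entirely on assumed correlations, and they apply to the daily score or its absolute change. Percent change was not sized.

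It is tempting to turn the variance cut into a power gain for a given study day. The documents do not support that: no single day has a power target, and the p-values are nominal. The primary endpoint, the Family 1 tests and type I error are unaffected.

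**What to change.** In SAP 12.3, for the daily WI-NRS ANCOVA only, add the mean of the available scores from the 7 days before dosing as a covariate, next to the last pre-dose daily score. Waive the 4-of-7 rule for this covariate alone so that sparse diaries do not drop a subject. If the only pre-dose score is older than 7 days, let that score stand in for the mean. Leave the daily baseline in SAP 5.2 unchanged for change, percent change and plots, and leave the weekly baseline and the WI-NRS population as defined.

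The cost is a sentence or two in the SAP, one model term and one degree of freedom. No new data are needed. The change should be fixed before unblinding.

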6.15. Pharmacokinetic Analysis

Plasma drug concentrations will be summarized using descriptive statistics, reporting n, mean, standard deviation, median, minimum, and maximum. The PK population will be used for these analyses.

7. STUDY ADMINISTRATION

7.1. Ethics

7.1.1. Ethics Review Board

Before screening of subjects into the study, the current protocol, ICF, and any accompanying material to be provided to the subjects will be reviewed and approved by an appropriate IRB, as required by FDA (21 CFR § 56) and ICH GCP regulations. A letter documenting the IRB approval must be received by the Sponsor before the initiation of the study at a clinical site. Amendments to the protocol will be subject to the same requirements as the original protocol.

The Investigator, Sponsor, or designee will submit a progress report at least once yearly to the IRB. However, the frequency of these reports will depend on IRB requirements. As soon as possible after completion or termination of the study, the Investigator will submit a final report to the IRB per the IRB requirements, and in compliance with FDA and ICH GCP guidelines.

The Investigator, the Sponsor, or designee shall promptly notify the IRB of any SAEs, SUSARs, or any other information that may affect the safe use of the study drug(s) during the study, per the IRB local requirements, and in compliance with FDA regulations and ICH GCP guidelines.

7.1.2. Ethical Conduct of the Study

This research will be carried out in accordance with the protocol, the principles of the Tri-Council Policy Statement (TCPS), the ethical principles set forth in the Declaration of Helsinki, and the ICH harmonized tripartite guideline regarding GCP (E6 Consolidated Guidance, April 1996).

7.1.3. Subject Information and Consent/Assent

The investigator is responsible for obtaining written informed consent from each individual participating in this study after adequate explanation (in non-technical terms) of the aims, methods, objectives, and potential hazards of the study and before undertaking any study-related procedures. The investigator must use the most current IRB- or IEC-approved consent form for

Confidential

documenting written informed consent. Subjects will be assured that they may withdraw from the study at any time without jeopardizing their medical care. Each informed consent (or assent as applicable) will be read, appropriately signed and dated by the subject or the subject's legally authorized representative and the person conducting the consent discussion, and also by an impartial witness if required by IRB or IEC or local requirements.

Subjects will be given a signed copy of their ICF/assent.

7.2. Study Completion and Termination

7.2.1. Study Completion

The study is considered completed with the last visit of the last subject participating in the study. The final data from the investigational site will be sent to the Sponsor (or designee) after completion of the final subject visit at that site, in the time frame specified in the Clinical Trial Agreement.

7.2.2. Study Termination

The Sponsor reserves the right to close the investigational site or terminate the study at any time for any reason at the sole discretion of the Sponsor. Investigational sites will be closed upon study completion. An investigational site is considered closed when all required documents and study supplies have been collected and a site closure visit has been performed. The investigator may initiate site closure at any time, provided there is reasonable cause and sufficient notice is given in advance of the intended termination.

Reasons for the early closure of an investigational site by the Sponsor or investigator may include but are not limited to:

- Failure of the investigator to comply with the protocol, the Sponsor's procedures, or GCP guidelines.
- Inadequate recruitment of subjects by the investigator.
- Discontinuation of further drug development.

